To assess the generalizability of the data from the patients enrolled, the physician will be asked to document on a separate Case Reporting Form the number of patients who are eligible but refuse to participate in the study. Only age ranges (<30 years, 30-45 years, 45-65 and > 65 years) and reason(s) for not participating will be collected.

The primary endpoint of this PMOS will be the percentages of APD patients on LCIG monotherapy right after LCIG initiation and at 3, 6, 9, and 12, respectively.

The secondary endpoints are:

- Descriptive data from patient's PD medication:
 - For add-on PD medication: percentage of patient on each PD medication (by drugs and class), total daily dose and levodopa equivalent Daily dose (LEDD), posology (number of times per day);
 - For LCIG infusion settings and substantial dose adjustments: total dose per day and specific for each type of dose (morning dose and continuous dose) and number of hours of infusion.

- Tapering process: number of days required for the tapering process, total dose per day and posology for add-on PD medication prior to LCIG initiation, at LCIG initiation (titration) or during ongoing LCIG treatment
- Main reasons for introduction or tapering of add-on PD medication or LCIG substantial dose adjustments
- Latency and duration of treatments data:
 - Number of days or months from LCIG initiation until LCIG is given as a monotherapy and the duration of LCIG monotherapy.
 - Number of days or months from LCIG initiation until the introduction or tapering of each PD medication, or until any LCIG substantial dose adjustments.
- LCIG monotherapy vs LCIG plus add-on PD medication data:
 - Healthcare Resource Utilization, as measured by Healthcare Resource Utilization Questionnaire (HCRU)
 - Patient's, caregiver's, and physician's overall preference on LCIG monotherapy vs. LCIG plus add-on PD medication, percentage of patient's and physician's preference for each of the options
 - Predictors for LCIG as monotherapy vs. LCIG plus add-on PD medication based on the patient's profile, including socio-demographics, clinical status (motor and non-motor symptoms), Levodopa-equivalent dose (LED), PD medication and Quality of Life
 - Predictors for LCIG as monotherapy vs. LCIG plus add-on PD medications based on the physician's profile including experience as measured by number of years on APD patient management, number of years using LCIG therapy, and number of patients on LCIG therapy

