## 3.2 Secondary objectives

The secondary objectives of this study are:

- To describe PD medication management, and the main reasons justifying their use, directly prior to LCIG initiation, at LCIG initiation and during long-term LCIG treatment
- To describe LCIG infusion settings and substantial dose adjustments and the respective reasons
- To describe the Healthcare Resource Utilization (HCRU)
- To identify the physician's and patient's/caregiver's overall preference for the pharmacological treatment approach using LCIG as monotherapy vs. LCIG plus add-on PD medication
- To identify predictors for achieving long-term monotherapy with LCIG vs. LCIG plus add-on PD medication, based on the patient's profile and the physician's profile
- To describe the latency from LCIG initiation until LCIG is given as a monotherapy and the average duration of LCIG monotherapy
- To describe the latency from the initiation of LCIG therapy until the introduction or tapering of each PD medication, or until substantial dose adjustments of LCIG
- To evaluate the percentage of patients who are on LCIG monotherapy, PD medication management and HCRU for the participating countries who have enrolled a minimum of 20 study subjects

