## 5 Analysis data set

One analysis set will be used:

The full analysis set (FAS) consists of all patients enrolled who fulfill the patient selection criteria.

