#### 6.2 Physician's profile

- Therapeutic specialty (type)
- Number of years physician has been working at the institution
- Approximate number of PD patients treated per year
- Approximate number of APD patients treated per year
- Approximate number of APD patients treated with LCIG per year
- Use of standard treatment algorithms/established guidelines/definitions of PD treatment (yes, no)
  - If yes: specification (multiple answers)
- Overall treatment preference
- Years of DBS experience
- Number of DBS patients
- Years of CSAI experience
- · Number of CSAI patients

Years of LCIG experience

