- Number of pills in addition to LCIG the patient would be willing to take each day
- Problems before starting LCIG (multiple answers)
- Help required to remember to take the medication (yes, no)
- Influence on the patient's decision to start treatment with LCIG (yes, no, missing)
  - If not 'no':
    - Doctor
    - Caregiver
    - Other family member
- Any scheduled visits with the treating physician for PD (yes, no)
- Any extra or unscheduled visits with the treating physician for PD (yes, no)
- Been seen in the Emergency Room due to PD (yes, no)
- Hospitalization (yes, no)
  - If yes: due to PD (yes, no)
- Overall treatment preference from physician's profile (LCIG as monotherapy, LCIG plus add-on PD medication)

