## 7 Statistical methodology

## 7.1 General methodology

All statistical analyses will be carried out by means of the SAS® package (version 9.4).

Quantitative data (e.g. age) will be described by the statistical parameters valid N, missing N, mean, standard deviation (SD), minimum, the 25%-quartile, median, the 75%-quartile, and the maximum.

Qualitative data (e.g. gender) will be presented by means of (absolute and relative) frequency distributions. If applicable, two methods will be followed for calculation of percentages. The first method considers missing data as a separate group, which results in the same sample size for all parameters. The second method of calculation is based on the valid data per parameter, excluding patients with missing values ("valid data analysis"). Accordingly, this results in different sample sizes. In general, description of results within the report refers to the "valid data analysis".

For categorical variables associated with score values, the mean will be calculated as well.

Two-sided 95% confidence intervals will be provided for the primary, and if applicable, the secondary variables defined by proportions.

Statistical methods which differ from the above mentioned methods or require further description will be addressed in the following sections.

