#### 7.6 Secondary variables

The secondary variables will be evaluated for FAS.

Secondary variables will be analyzed overall and separately for the following three groups:

- Patients on monotherapy 1 at 12 months after LCIG infusion (see Section 6.4)
- Patients on monotherapy 2 at 12 months after LCIG infusion (see Section 6.4)
- Patients not on monotherapy 2 at 12 months after LCIG infusion (see Section 6.4)

Regarding 'Add-on PD medication' patient based means that a therapy type will only be counted once per patient. The variables total daily dose, LEDD and posology will additionally be analyzed per category by summing up the values of the corresponding medication/therapy.

Regarding total dose per day the difference will be calculated between the time points LCIG initiation start, 12 months after LCIG initiation start and visit as follows:

- Total dose per day at 12 months after LCIG initiation start minus total dose per day at LCIG initiation start
- Total dose per day at visit minus total dose per day at LCIG initiation start
- Total dose per day at visit minus at 12 months after LCIG initiation start

If applicable, levodopa equivalent daily dose (LEDD) will be calculated separately for each medication/therapy as total daily dose in mg multiplied with the respective factor (from Table 7-1; [1], [2], [3]). Exceptions are entacapone, tolcapone and opicapone: irrespective of the entacapone dose (or tolcapone or opicapone dose, respectively) the corresponding levodopa dose is multiplied by the given factor. This will then be considered as LEDD for entacapone (or tolcapone or opicapone, respectively).

The total daily LEDD will be the sum over all daily LEDDs which were calculated separately for each medication at the respective time point.

Table 7-1: Factor for levodopa equivalent daily dose

Medication	Factor
Levodopa/carbidopa	1.11
Levodopa/benserazide	1
Levodopa/carbidopa/entacapone	1.33
Amantadine	1
Apomorphine	10
Cabergoline	80
Entacapone	concomitant levodopa multiplied by 0.33
Tolcapone	concomitant levodopa multiplied by 0.5
Pramipexole	100
Rasagiline	100
Ropinirole	20
Rotigotine	30
Selegiline oral	10
Opicapone	concomitant levodopa multiplied by 0.65
Safinamide	
Budipine	5

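### The physician-preference secondary endpoint falls under the patient-based FAS rule, so its percentage is weighted by enrolment and any interval on patient rows would be too narrow for physicians

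*SAP*

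**What the plan says.** The objective in SAP 3.2 reads "To identify the physician's and patient's/caregiver's overall preference for the pharmacological treatment approach". The protocol (Abstract and 9.1) makes the endpoint the "percentage of patient's and physician's preference for each of the options".

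In the SAP the item appears twice:

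- **As a physician variable.** SAP 6.2 lists "Overall treatment preference" in the physician's profile. SAP 7.3 presents the characteristics of the participating physicians by reference to 6.2.
- **As a secondary variable.** SAP 6.5, under the comparison of LCIG monotherapy with LCIG plus add-on medication, lists "Overall treatment preference from physician's profile (LCIG as monotherapy, LCIG plus add-on PD medication".

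For the second listing, SAP 7.6 states: "The secondary variables will be evaluated for FAS". It makes no exception for this item and asks for results overall and in three patient groups, the first being "Patients on monotherapy 1 at 12 months after LCIG infusion (see Section 6.4". SAP 5 fixes the unit: "The full analysis set (FAS) consists of all patients enrolled who fulfill the patient selection criteria".

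On intervals, SAP 7.1 says: "Two-sided 95% confidence intervals will be provided for the primary, and if applicable, the secondary variables defined by proportions". Protocol 9.7 has the same rule for primary and secondary endpoints that are proportions, without the qualifier. Neither document gives a cluster adjustment.

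**The concern.** The preference is an attribute of the physician, recorded once. The analysis rule that applies to the endpoint counts patients. Eligible patients are enrolled consecutively at each site (SAP 4.2), and each must have had the same treating physician since LCIG was started (inclusion criterion 3). Several rows can therefore carry one physician's answer.

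Two things are at stake. First, the percentage becomes the share of patients whose physician holds a given preference. That differs from the share of physicians whenever preference is related to the number of patients enrolled. Second, an interval built on about 400 rows treats copies of one answer as independent observations. A named secondary objective could then be answered with precision that the data do not have, alongside a different percentage from the 7.3 table and with no statement of which figure is the endpoint.

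**Working it through.** **1. Which unit do the rules imply?** No sentence says that physicians are counted once per patient; this follows from SAP 5 and 7.6 together. The grouping supports it. A physician cannot be on monotherapy at 12 months, so the by-group table can be built only by attaching the physician's answer to each patient. SAP 2.5 makes the SAP's methods mandatory for programming. The SAP marks some other variables as patient based or event based, but gives no unit here.

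**2. Inputs.** About 400 planned patients (SAP 4.2). Required evaluable patients 385, underlying percentage 50%, two-sided 95% interval of ±5 points (Protocol 9.5). The number of physicians, k, is not in the documents; k = 15 to 100 is assumed.

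**3. The plan's own figure.** n = 1.96² × 0.25 / 0.05² = 384.15, rounded up to 385. This reproduces the protocol, so the same normal-approximation formula is used below.

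**4. Half-widths at 50%.** On patient rows: 1.96 × √(0.25/400) = 4.9 points. With one record per physician: 1.96 × √(0.25/k). Because the answer is constant within a physician, the intracluster correlation is 1. With equal enrolment the design effect is therefore 400/k, and the patient-row interval is too narrow by a factor of √(400/k).

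| k (assumed) | Patients per physician | Half-width, physicians (points) | Half-width, 400 rows (points) | Ratio |
|---|---|---|---|---|
| 15 | 26.7 | 25.3 | 4.9 | 5.2 |
| 30 | 13.3 | 17.9 | 4.9 | 3.7 |
| 50 | 8.0 | 13.9 | 4.9 | 2.8 |
| 100 | 4.0 | 9.8 | 4.9 | 2.0 |

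**5. Coverage.** For equal enrolment, the number of physicians preferring monotherapy was taken as binomial(k, p), and the probability that the patient-row interval contains p was summed exactly. Averaged over p from 30% to 70%, coverage is about 29% (k = 15), 40% (k = 30), 51% (k = 50) and 67% (k = 100), against the nominal 95%.

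**6. Shift of the estimate (illustration; all inputs assumed).** Suppose 10 physicians enrol 25 patients each and 80% of them prefer monotherapy, while 30 physicians enrol 5 each and 40% prefer it.

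- Patient rows: (10 × 25 × 0.8 + 30 × 5 × 0.4)/400 = 260/400 = 65%.
- Physicians: (10 × 0.8 + 30 × 0.4)/40 = 20/40 = 50%.

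The documents do not say whether enrolment and preference are related. If they are not, the estimate is not shifted in expectation and only the interval problem remains.

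**The case against.** The strongest reply is that a physician-level result is already planned. SAP 6.2 contains the item and 7.3 presents it, so a reader who inferred that the report will hold no percentage describing physicians would be wrong. This stands. It does not settle the matter, because the SAP attaches the label of secondary variable to the 6.5/7.6 version. The interval rule in 7.1 covers primary and secondary variables, not profile items. Read literally, the table with the right unit gets no interval, and the table with the wrong unit is the one eligible for it.

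Second, the patient-row table may be intended. Its place under the monotherapy comparison suggests a description of what share of patients in each group have a physician who prefers monotherapy. That is a legitimate question and needs patient rows, since one physician can have patients in several groups. This stands too: for the by-group table the defect is labelling and the basis of any interval, not the table itself.

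Third, a reader might infer that a too-narrow interval is certain to be printed. The SAP does not support that, because its rule for secondary proportions applies only where applicable. Protocol 9.7 is unconditional and the SAP claims consistency with it, so an interval is foreseeable but not specified for this item.

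Fourth, a physician-based interval is not exact either. Sites are chosen for experience with advanced disease and with LCIG (Protocol 9.2.2), and physicians are nested in sites and countries. The formula treats them as a simple random sample. It has the right unit for the endpoint, but it does not remove every dependence.

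**Conclusion.** The concern holds in this form: under SAP 6.5, 7.6 and 5, the percentage labelled as the physician-preference secondary endpoint is computed on patient rows and weighted by enrolment. Any 95% interval based on those rows would be too narrow for physicians, by a factor of 2.0 with 100 physicians up to 5.2 with 15.

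The size rests on an assumed number of physicians, on 50% preference, on 400 rows and on equal enrolment. A single multiplier such as three should not be quoted, because it only reflects the number of physicians chosen. Any shift in the point estimate is possible but not shown; it needs preference to vary with enrolment.

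This is one descriptive secondary item in a study that SAP 7.10 calls exploratory, and no primary result is affected. It is still more than a missing detail, because the written rule gives the wrong unit for a named endpoint and leaves two percentages without saying which one answers it.

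**What to change.** In SAP 6.5 and 7.6, exempt this item from the FAS rule. State that the endpoint is reported with one record per participating physician, in the 7.3 table, with a two-sided 95% confidence interval on the number of physicians, and that this table answers the objective in 3.2.

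If the breakdown by monotherapy group is kept in the FAS, label it *patients whose physician prefers …* and give either no interval or one clustered on physician. The same applies to any interval for a difference between groups, since one physician's answer can appear in both.

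The cost is a few lines of SAP text and a data step that keeps one record per physician. The downside is a wider interval for the endpoint.

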## 6.6 Reportable events and product complaints

- Separately for 'LCIG initiation' and 'LCIG Maintenance Treatment':
  - Any adverse reaction (yes, no; patient based)
  - Event diagnosis (MedDRA coding; patient based)
  - Action taken (event based)
- Events occurring after the time of patient authorization:
  - Reportable event (patient based):
    - Any adverse event (AE)
    - Serious adverse events (SAE)
    - Adverse drug reaction (ADR)
  - Event diagnosis (MedDRA coding; patient based): separately for AE, SAE, ADR
  - Any pregnancy which has not been reported to an AbbVie care Duodopa nurse (yes, no)
  - Any product complaint that has not been reported before (yes, no)
    - If yes: Complaint description (MedDRA coding; patient based)

#### 6.7 Missing data and outliers

The handling of missing single items in rating scales is described in Sections 4.4.4 and 4.4.5.

## 7 Statistical methodology

## 7.1 General methodology

All statistical analyses will be carried out by means of the SAS® package (version 9.4).

Quantitative data (e.g. age) will be described by the statistical parameters valid N, missing N, mean, standard deviation (SD), minimum, the 25%-quartile, median, the 75%-quartile, and the maximum.

Qualitative data (e.g. gender) will be presented by means of (absolute and relative) frequency distributions. If applicable, two methods will be followed for calculation of percentages. The first method considers missing data as a separate group, which results in the same sample size for all parameters. The second method of calculation is based on the valid data per parameter, excluding patients with missing values ("valid data analysis"). Accordingly, this results in different sample sizes. In general, description of results within the report refers to the "valid data analysis".

For categorical variables associated with score values, the mean will be calculated as well.

Two-sided 95% confidence intervals will be provided for the primary, and if applicable, the secondary variables defined by proportions.

Statistical methods which differ from the above mentioned methods or require further description will be addressed in the following sections.

#### 7.2 Site information

The number of participating sites (e.g. sites with at least one patient) and a summary of characteristics of the sites will be presented (see Section 6.1).

#### 7.3 Physician's profile

The characteristics of the participating physicians will be presented (see Section 6.2).

#### 7.4 Patient data

Patient disposition will be evaluated for all patients enrolled.

All other variables will be evaluated for FAS according to the methods described in Section 7.1.

Patient data will be analyzed overall and separately for the following three groups:

- Patients on monotherapy 1 at 12 months after LCIG infusion (see Section 6.4)
- Patients on monotherapy 2 at 12 months after LCIG infusion (see Section 6.4)

Patients not on monotherapy 2 at 12 months after LCIG infusion (see Section 6.4) For duration of 'Off' state (hours) and duration of dyskinesia (hours) the difference will be calculated between the time points 'prior to LCIG initiation' and visit (UPDRS IV: modified items 39 and 32) as value at visit minus value prior to LCIG initiation.

'Other' co-morbidities will be coded using MedDRA. Incidence rates will be calculated with respect to System Organ Class and Preferred Term.

Regarding the 'Historical therapy discontinued prior to considering LCIG initiation' patient based means that a therapy type will only be counted once per patient.

A list of other medications and therapies only for indications secondary to PD will be provided including the following information:

- PatientID
- Name of concomitant medication or therapy
- Indication
- Total daily dose
- Dose unit
- Start date
- End date
- Ongoing at the end of study

## 7.5 Primary variable

The primary variable will be evaluated for FAS.

For the time period between 12 months after LCIG initiation and the visit, appropriate time points will be used.

#### 7.6 Secondary variables

The secondary variables will be evaluated for FAS.

Secondary variables will be analyzed overall and separately for the following three groups:

- Patients on monotherapy 1 at 12 months after LCIG infusion (see Section 6.4)
- Patients on monotherapy 2 at 12 months after LCIG infusion (see Section 6.4)
- Patients not on monotherapy 2 at 12 months after LCIG infusion (see Section 6.4)

Regarding 'Add-on PD medication' patient based means that a therapy type will only be counted once per patient. The variables total daily dose, LEDD and posology will additionally be analyzed per category by summing up the values of the corresponding medication/therapy.

Regarding total dose per day the difference will be calculated between the time points LCIG initiation start, 12 months after LCIG initiation start and visit as follows:

- Total dose per day at 12 months after LCIG initiation start minus total dose per day at LCIG initiation start
- Total dose per day at visit minus total dose per day at LCIG initiation start
- Total dose per day at visit minus at 12 months after LCIG initiation start

If applicable, levodopa equivalent daily dose (LEDD) will be calculated separately for each medication/therapy as total daily dose in mg multiplied with the respective factor (from Table 7-1; [1], [2], [3]). Exceptions are entacapone, tolcapone and opicapone: irrespective of the entacapone dose (or tolcapone or opicapone dose, respectively) the corresponding levodopa dose is multiplied by the given factor. This will then be considered as LEDD for entacapone (or tolcapone or opicapone, respectively).

The total daily LEDD will be the sum over all daily LEDDs which were calculated separately for each medication at the respective time point.

Table 7-1: Factor for levodopa equivalent daily dose

Medication	Factor
Levodopa/carbidopa	1.11
Levodopa/benserazide	1
Levodopa/carbidopa/entacapone	1.33
Amantadine	1
Apomorphine	10
Cabergoline	80
Entacapone	concomitant levodopa multiplied by 0.33
Tolcapone	concomitant levodopa multiplied by 0.5
Pramipexole	100
Rasagiline	100
Ropinirole	20
Rotigotine	30
Selegiline oral	10
Opicapone	concomitant levodopa multiplied by 0.65
Safinamide	
Budipine	5

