#### 6.4 Primary variable

There are two primary variables:

1. LCIG monotherapy 1 (yes, no) at LCIG initiation and at 3, 6, 9, and 12 months after LCIG initiation

with the following definition:

- LCIG monotherapy means that the patient is not on any add-on PD medication or PD therapy at the respective time point.
- 2. LCIG monotherapy 2 (yes, no) at LCIG initiation and at 3, 6, 9, and 12 months after LCIG initiation

with the following definition:

LCIG monotherapy means that the patient is allowed to take an add-on PD medication or PD therapy at the respective time point, however, only in the evening after the LCIG infusion is completed (i.e. reason for start of add-on PD medication: other).

Additional specifications for both variables are:

- Medications for indications secondary to PD are allowed.
- If the reason for add-on PD medication is missing the medication will be considered as taken during LCIG infusion (i.e. no monotherapy).
- LCIG initiation date is the start date of the first LCIG infusion.
- 3 months after LCIG initiation is calculated as LCIG initiation date + rounded (3 [months] x 30.4 [days]). 6, 9, and 12 months after LCIG initiation will be calculated analogously.
- For LCIG initiation date with missing day the 15th will be used.

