#### Reasons:

- For each add-on PD medication/therapy at the time points LCIG initiation and at 3, 6, 9, and 12 months after LCIG initiation and at visit::
  - Reason for start (multiple answers)
  - If not ongoing: reason for discontinuation (multiple answers)
- Reason for change on LCIG dose in general
- Reason for LCIG dose changes (multiple answers) by 5%, 10%, 15%, 20% or 25% or higher
- Reason for substantial LCIG dose changes (multiple answers) with substantial change defined as any increase or decrease of the total daily LCIG dose by more than 20%
- Latency and duration of treatments:
  - For patients with add-on PD medication or PD therapy at LCIG initiation: Time from LCIG initiation until LCIG is given as a monotherapy (separately for monotherapy 1 and monotherapy 2 definition)

[figure not shown]
Only patients with add-on PD medication or PD therapy at LCIG initiation

 For patients with add-on PD medication or PD therapy at LCIG initiation and separately for patients with and without ongoing monotherapy at visit: Duration of LCIG monotherapy (separately for monotherapy 1 and monotherapy 2 definition) Only patients with add-on PD medication or PD therapy at LCIG initiation Analysis a) Without ongoing monotherapy until visit

Analysis b) With ongoing monotherapy until visit

- For each add-on PD medication/therapy:
   Time from LCIG initiation until the respective add-on PD medication/therapy is started or changed
- Time from LCIG initiation until the first LCIG dose change by 5%, 10%, 15%, 20% or 25%
- Time from LCIG initiation until the first substantial LCIG dose change with substantial change defined as any increase or decrease of the total daily LCIG dose by more than 20% in relation to first LCIG infusion
- LCIG monotherapy (1 and 2) vs. LCIG plus add-on PD medication:
  - o HCRU:
    - Primary occupation (retired, on sick leave, unemployed, working full time, working part-time, student)
      - If retired: due to PD (yes, no)
      - If on sick leave: due to PD (yes, no)
      - If unemployed: due to PD (yes, no)
    - Permanent living in a nursing home/institution (yes, no)
    - Help in daily activities
    - Frequency of visits:
      - General practitioner

- Nurse
- Occupational/speech therapist
- Physiotherapist
- Psychologist and/or psychiatrist
- Dietician
- Discussion of LCIG monotherapy (yes, no, patient did not remember)
- Offering of LCIG monotherapy (yes, no, patient did not remember)

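### SAP 7.6 breaks latency to monotherapy and its duration down by month-12 monotherapy status, which these variables help determine, so groups differ even if all patients are identical

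*SAP*

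**What the plan says.** SAP 7.6 sets one rule for all secondary variables: "Secondary variables will be analyzed overall and separately for the following three groups". The groups are patients on monotherapy 1, patients on monotherapy 2, and patients not on monotherapy 2, each judged at 12 months. SAP 6.4 gives the first status: "LCIG monotherapy means that the patient is not on any add-on PD medication or PD therapy at the respective time point". Monotherapy 2 also allows an add-on in the evening after the infusion ends.

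SAP 6.5 lists these secondary variables under latency and duration of treatments:

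- "Time from LCIG initiation until LCIG is given as a monotherapy", for each definition.
- Duration of monotherapy, shown separately for episodes ended and episodes ongoing at the visit.
- "Time from LCIG initiation until the respective add-on PD medication/therapy is started or changed", for each add-on.
- Time to LCIG dose changes.

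The first two carry a restriction: "Only patients with add-on PD medication or PD therapy at LCIG initiation". SAP 7.6 exempts none of these variables. No landmark, censoring rule or time-to-event method is given for them.

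**The concern.** The add-on start and stop dates that give a patient's latency and duration also decide the month-12 group. The split therefore conditions an interval that begins before month 12 on a status that the interval helps to fix.

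A table built this way would show month-12 monotherapy patients reaching monotherapy sooner and keeping it longer. A reader could take that as a feature of the patients or their management, although the grouping rule alone produces a contrast in that direction. Protocol 9.7 foresees confidence intervals for differences between monotherapy and add-on groups where appropriate, which would give the contrast more apparent weight.

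**Working it through.** **Plan's own figure.** The documents give no figure for latency or duration. The only computed design figure is the sample size, and it reproduces: 1.96² × 0.5 × 0.5 / 0.05² = 384.2, rounded up to 385. This point does not affect it.

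**Step 1: what follows from the definitions alone.** By SAP 6.4, month 12 is initiation plus round(12 × 30.4) = round(364.8) = 365 days. Patients in the latency analysis have an add-on at day 0, so none is then on monotherapy 1. To be on it at day 365, a patient must have started an episode by day 365 that is still running. Every first latency in that group is therefore at most 365 days, and any first latency above 365 days falls outside it. Patients outside it reached monotherapy later, lost it before month 12, or never reached it. The last have no latency value, and no censoring rule covers them. For monotherapy 2 the same bound holds for patients who do not already meet that definition at initiation.

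**Step 2: closed form for identical patients.** Assume one constant rate with an overall median of 365 days, no relapse and unlimited follow-up. Then λ = ln 2 / 365, and half the patients are on monotherapy at day 365.

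- Median given latency ≤ 365: solve 1 − exp(−λt) = 0.25, so t = −ln(0.75)/λ = 151 days.
- Median given latency > 365: 365 + 365 = 730 days.

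**Step 3: identical patients with relapse and limited follow-up (simulation).** All rates and follow-up times are assumed, because the documents give only the 12-month minimum. One monotherapy definition is used throughout.

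| Assumption | On monotherapy at month 12 | Not on it |
|---|---|---|
| Median 6-24 months to leave add-on, 12-48 months to restart, visit at 1-8 years: median latency | about 130-200 days | about 400-770 days |
| 40% reach monotherapy by month 12, no stopping, visit at 12-60 months: mean latency | 5.5 months | 23.4 months |
| Same: mean duration | 30.5 months | 18.3 months |
| As above, but mean time on monotherapy 24 months: mean latency | 5.9 months | 19.7 months |
| Same: mean duration | 18.9 months | 10.1 months |

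Early onset is plausible. Protocol 7.0 reports add-on use falling from 89% to 37% by day 1 of an extension study. If 60-80% leave add-ons around titration (mean 14 days), the median latency gap runs from a few days (12 versus 15 in the smallest case) to over 400 days when restart is rare. In that smallest case median duration still differed, 552 versus 175 days.

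The median duration gap was roughly 330-760 days across the constant-rate and early-onset scenarios. A separate set counted the first episode, cut at the visit, with visits at 12-36 or 12-60 months. There the mean duration gap was 4 to 15 months and the mean latency gap 4 to 21 months. The direction was the same in every scenario of that set.

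**Step 4: add-on started or changed.** If stopping counts as a change, pooled medians were 257 days (monotherapy at month 12) versus 403 days, with 365-day medians to leave and to restart. If only starts count, the order reverses: means of 23.3 versus 5.5 months, with 40% starting by month 12 and no stopping. The variable is tied to the status, but its direction depends on how a change is read.

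**Step 5: negative control.** An LCIG dose-change latency simulated independently of the status showed a mean group difference of −0.04 to 0.02 months. The distortion is specific to variables that enter the status.

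**The case against.** The strongest reply is that nothing inferential is planned. The objectives only describe latency. SAP 6.5 lists latency apart from the comparison of monotherapy with add-on treatment, and SAP 7.1 provides intervals for proportions only. The unsplit analysis is also planned and answers the objective. All of this stands, and it limits the harm to how the group tables are read. It also shows that the protocol does not need this split for latency. SAP 7.6 still requires the tables, and SAP 2.5 makes its methods mandatory for programming, although SAP 7.10 permits changes.

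SAP 6.5 already separates ended from ongoing episodes, but that does not remove the contrast. With 40% reaching monotherapy by month 12, mean time on monotherapy 12 months and visits at 12-60 months, mean duration was 12.7 versus 6.0 months for ended episodes and 16.8 versus 9.5 for ongoing ones.

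The objection on size also stands: with onset concentrated around titration the latency gap can almost vanish.

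Finally, how long month-12 monotherapy patients took to get there is a legitimate description of that one group. Only the contrast is uninformative.

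**Conclusion.** The point holds for latency to monotherapy and duration of monotherapy. The 365-day bound on latency in the monotherapy 1 group follows from the definitions. The size rests on assumed onset, relapse and follow-up patterns, and runs from a few days to more than a year for median latency. Time to add-on start or change should also leave the split, with no direction claimed.

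A reader might infer more than the documents support:

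- *Month-12 monotherapy patients will appear to start add-ons later.* The SAP variable covers starts and changes, and the direction can go either way.
- *The latency gap will necessarily be large.* It need not be with early onset.
- *All these variables run from day 0.* Duration does not; for patients with an add-on at initiation, a monotherapy 1 episode begins later.
- *Every secondary variable is affected.* LCIG dose-change latency is not a component of the status and needs no exemption.
- *The latency objective or the primary endpoint is compromised.* The overall analysis and the primary endpoint are untouched.

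This is a correction worth making to the SAP, not a flaw in the main result.

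**What to change.** In SAP 7.6, exempt three variables from the month-12 split: latency to monotherapy, duration of monotherapy, and time to add-on start or change. Report them overall. Report add-on start latency also by monotherapy status at LCIG initiation, which precedes the event.

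If a month-12 breakdown is wanted, use month 12 as a landmark. Report time from month 12 to first add-on in patients on monotherapy then, and time from month 12 to monotherapy in those not on it, both censored at the visit.

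The cost is SAP wording and a few changed tables. The time that month-12 monotherapy patients took to reach monotherapy leaves the comparison tables; it can be kept as a one-group description without a contrast. The landmark analysis answers a different question, and patients visited near month 12 add little follow-up to it.
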